6.6.3. Recommended Pembrolizumab Dose Modifications for the Management of Pembrolizumab Toxicities

Non-hematologic and hematologic AEs for pembrolizumab for non-overlapping toxicities in combination with duvelisib should be managed as described in the current pembrolizumab prescribing information ([Keytruda 2019](#)). The general recommendations cited in the June 2019 pembrolizumab prescribing information are summarized in [Table 13](#).

Table 13: Recommended Pembrolizumab Dose Modifications for the Management of Pembrolizumab Toxicities

Adverse Reaction	Severity ^a	Dose Modification	Recommended Management
Immune-mediated hypophysitis (including hypopituitarism and adrenal insufficiency)	Grade 2 hypophysitis	Withhold dose until clinically stable	Treat with corticosteroids and hormone replacement as clinically indicated
	Grade 3 or 4 hypophysitis	Withhold dose until clinically stable or permanently discontinue	
Immune-mediated thyroid disorders	Grade 2 thyroid disorders	No change in dose	Administer replacement hormones for hypothyroidism and manage hyperthyroidism with thionamides and beta-blockers as appropriate
	Grade 3 or 4 thyroid disorders	Withhold dose until clinically stable or permanently discontinue	

Adverse Reaction	Severity ^a	Dose Modification	Recommended Management
Immune-mediated type 1 diabetes mellitus	Grade 3 or 4 hyperglycemia	Withhold dose until clinically stable	Administer insulin for type 1 diabetes and administer anti-hyperglycemics in subjects with severe hyperglycemia
Immune-mediated nephritis and renal dysfunction	Grade 2	Withhold dose	Treat with corticosteroids (1 to 2 mg/kg/day prednisone or equivalents followed by a taper)
	Grade 3 or 4	Permanently discontinue	
Other immune-mediated adverse reactions	Grade 2 or 3 based on the severity and type of reaction	Withhold dose	Administer corticosteroids ^b Based on limited data from clinical studies in subjects whose immune-related adverse reactions could not be controlled with corticosteroid use, administration of other systemic immunosuppressants can be considered.
	Grade 3 based on the severity and type of reaction or Grade 4	Permanently discontinue	
Recurrent immune-mediated adverse reactions	Recurrent Grades 3 or 4	Permanently discontinue	
Inability to taper corticosteroid dosage	Requirement for ≥ 10 mg per day prednisone or equivalent for > 12 weeks after last dose of pembrolizumab	Permanently discontinue	

Adverse Reaction	Severity ^a	Dose Modification	Recommended Management
Persistent Grade 2 or 3 adverse reaction (excluding endocrinopathy)	Persistent Grade 2 or 3 adverse reactions lasting ≥ 12 weeks after last dose of pembrolizumab	Permanently discontinue	

Abbreviations: ALT: alanine aminotransferase; AST: aspartate aminotransferase; NCI CTCAE: National Cancer Institute Common Terminology Criteria for Adverse Events; ULN: upper limit of normal.

^a Severity was graded per NCI CTCAE v4.

^b Upon improvement to Grade 1 or less, initiate corticosteroid taper and continue to taper over at least 1 month.

6.6.4. Management of Infusion-related Reactions

Infusion reactions (or suspected hypersensitivity infusion reaction and/or anaphylaxis) are defined below (Table 14).

Table 14: NCI CTCAE Grading for Infusion Reactions

Grade	Description
1	Mild transient reaction; infusion interruption not indicated; intervention not indicated
2	Therapy or infusion interruption indicated but responds promptly to symptomatic treatment (e.g., NSAIDS, narcotics, IV fluids); prophylactic medications indicated for ≤ 24 hrs.
3	Prolonged (e.g., not rapidly responsive to symptomatic medication and/or brief interruption of infusion); recurrence of symptoms after initial improvement; hospitalization indicated for clinical sequelae
4	Life-threatening consequences; urgent intervention indicated
5	Death

Abbreviations: IV: intravenous; NCI CTCAE: National Cancer Institute Common Terminology Criteria for Adverse Events; NSAID: nonsteroidal anti-inflammatory drug.

Study site policies shall be used for the management of infusion reactions.

Treatment should be permanently discontinued for severe and life-threatening infusion reactions. The rate of infusion should be slowed or interrupted in subjects with mild or moderate infusion reactions (Keytruda 2019).

6.7. DLT Evaluation

In Stage 1, the DLT evaluation period is Cycle 1 (4 weeks or 28 days): 1 week of duvelisib monotherapy lead-in followed by 3 additional weeks of duvelisib in combination with pembrolizumab. Every effort will be made to administer the first dose of pembrolizumab on Day 8 of Cycle 1 (C1D8). If the first dose of pembrolizumab on C1D8 is delayed, every effort should be made to delay the subsequent dosing of the next cycle (within the protocol allowed

window of 3 days) to achieve as close to a 3-week interval between pembrolizumab doses as possible. The Medical Monitor needs to be consulted for such adjustments to ensure uniformity of approach and to account for subject-specific circumstances. For example, if the third day of the C2D1 window falls on a weekend, an additional adjustment would need to be made on a case-by-case basis. In the event of a delay of the start of pembrolizumab therapy, DLTs will be evaluated at the end of the third week of combination therapy.

The DLT evaluation period will be used to assess DLTs in the first 6 subjects.

- If there is ≤ 1 DLT in the 6 DLT-evaluable subjects, additional subjects will be enrolled to bring the total dosed in Stage 1 to approximately 13 subjects
- If there are ≥ 2 DLTs in the first 6 subjects, enrollment at duvelisib 25 mg BID will stop. Enrollment would restart at a reduced duvelisib dose (15 mg BID) to assess DLTs at the lower dose (dose level -1; see [Table 6](#))

6.7.1. Definition of Dose-limiting Toxicity

Dose-limiting toxicity is defined as an AE that occurs during the initial 4-week period (DLT evaluation period, Cycle 1), is at least possibly related to duvelisib, and fulfills at least 1 of the following criteria:

- Grade 3 or higher febrile neutropenia or Grade ≥ 3 neutropenia with infection or Grade 4 neutropenia lasting more than 7 days
- Grade 4 thrombocytopenia or Grade 3 thrombocytopenia with clinically significant bleeding
- Grade 3 or Grade 4 treatment-related non-hematologic toxicity, except nausea, vomiting, diarrhea and elevations in ALT or AST, which will be considered dose-limiting only if the subject develops:
 - Grade 3 nausea, vomiting, or diarrhea lasting more than 48 hours despite use of appropriate therapy or Grade 4 vomiting or diarrhea
 - Grade 3 elevations in ALT or AST lasting longer than 1 week, Grade 4 elevation in ALT or AST, or any ALT or AST elevations that require permanent discontinuation of study treatment
 - Grade 3 elevations in bilirubin elevation $> 2 \times$ ULN ($> 2 \times$ baseline for subjects with Gilbert's syndrome) lasting longer than 1 week, Grade 4 elevation in bilirubin, or any elevations in bilirubin that require permanent discontinuation of study treatment
 - Alkaline phosphatase (ALP) elevations will be evaluated on a case-by-case basis by the study team in assessing whether there is a DLT
- Grade 3 hypersensitivity reaction lasting longer than 24 hours or Grade 4 hypersensitivity regardless of duration
- A DLT for cardiac dysfunction will include any heart failure that is Grade ≥ 2 NCI CTCAE (Version 5.0 or higher). The AE must be clinically significant and at least possibly related to the study drug in order to be considered a DLT
- Any other toxicity that does not meet the definition of a DLT but requires permanent discontinuation of study treatment or is of concern to the Investigator and Sponsor may be considered to be a DLT

In rare instances, an event may fall within the definition of a DLT, as defined above, but the event may not be considered a DLT (e.g., not clinically meaningful). If this occurs, the Investigator and Sponsor will review the event and supporting data, and the reasons for not considering the event to be a DLT will be clearly documented with supporting rationale. Toxicities will be graded and documented according to the NCI CTCAE (Version 5.0 or higher).

6.7.2. Subjects With a DLT

In general, a subject who experiences a DLT should discontinue the study interventions. However, if there is evidence that a subject who experiences a DLT has also derived clinical benefit from the study interventions, the Medical Monitor and Investigator will review the specifics of the case, and the subject may be allowed to continue on study at the same dose or at a lower dose level of duvelisib if the consensus judgment is that continued treatment is in the subject's best interest. Subjects should have recovered from toxicity to baseline or Grade 1 (except alopecia) before re-treatment. For a DLT due to low hemoglobin or thrombocytopenia, the subject's hemoglobin concentrations should have returned to baseline grade before re-treatment; transfusions of packed red blood cells to treat anemia are permitted.

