Toxicity	Adverse Reaction Grade	Dose Modification and Recommended Management
		
 For confirmed PJP, discontinue duvelisib
Hematologic Adverse Reactions		
Febrile neutropenia	Grade 3-4	
 Interrupt duvelisib until afebrile and resolution of Grade 3 or Grade 4 neutropenia to Grade ≤ 2 (ANC > 1.0 Gi/L) Monitor ANC at least weekly until > 1.0 Gi/L Resume at same dose (first occurrence) or at a reduced dose for subsequent occurrence
Neutropenia	ANC 0.5 to 1.0 Gi/L	
 Maintain duvelisib dose Monitor ANC at least weekly
	ANC less than 0.5 Gi/L	
 Withhold duvelisib. Monitor ANC until > 0.5 Gi/L Resume duvelisib at same dose (first occurrence) or at a reduced dose for subsequent occurrence (see Table 11)
Thrombocytopenia	Platelet count 25 to < 50 Gi/L (Grade 3) with Grade 1 bleeding	
 No change in dose Monitor platelet counts at least weekly
	Platelet count 25 to < 50 Gi/L (Grade 3) with Grade 2 bleeding or Platelet count < 25 Gi/L (Grade 4)	
 Withhold duvelisib Monitor platelet counts until ≥ 25 Gi/L and resolution of bleeding (if applicable) Resume duvelisib at same dose (first occurrence) or resume at a reduced dose for subsequent occurrence (see Table 11)

Toxicity	Adverse Reaction Grade	Dose Modification and Recommended Management
Non-hematologic Adverse Reactions During the Duvelisib Monotherapy Lead-in Only^a		
Non-infectious Diarrhea or colitis	Mild/moderate diarrhea (Grade 1-2, up to 6 stools per day over baseline) and responsive to antidiarrheal agents, OR Asymptomatic (Grade 1) colitis	
 • No change in dose • Initiate supportive therapy with antidiarrheal agents as appropriate • Monitor at least weekly until resolved
	Mild/moderate diarrhea (Grade 1-2, up to 6 stools per day over baseline) and unresponsive to antidiarrheal agents	
 • Withhold duvelisib until resolved • Initiate supportive therapy with enteric acting steroids (e.g., budesonide) • Monitor at least weekly until resolved • Resume at a reduced dose (see Table 11)

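### For some Cycle 1 DLTs, Section 6.7.2 and the dose-modification tables give different stop and restart rules, and no text says which governs

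*Combined protocol and SAP*

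**What the plan says.** Section 6.7.2 sets the default after a DLT: "In general, a subject who experiences a DLT should discontinue the study interventions". A subject with evidence of clinical benefit may continue, at the same or a lower duvelisib dose, if the Medical Monitor and Investigator agree that this is in the subject's interest. The recovery condition is: "Subjects should have recovered from toxicity to baseline or Grade 1 (except alopecia) before re-treatment". The section ends with a special case: "For a DLT due to low hemoglobin or thrombocytopenia, the subject's hemoglobin concentrations should have returned to baseline grade before re-treatment".

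Section 6.7.1 makes these hematologic events DLTs, if at least possibly related to duvelisib: febrile neutropenia of Grade 3 or higher; Grade 3 or higher "neutropenia with infection or Grade 4 neutropenia lasting more than 7 days"; and "Grade 4 thrombocytopenia or Grade 3 thrombocytopenia with clinically significant bleeding".

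Section 6.6 introduces its tables as general recommendations. In Table 12, for ANC 0.5 to 1.0 Gi/L the instruction is "Maintain duvelisib dose". For ANC below 0.5 it is to withhold, then "Monitor ANC until > 0.5 Gi/L", then resume. For febrile neutropenia it is "Interrupt duvelisib until afebrile and resolution of Grade 3 or Grade 4 neutropenia" to Grade 2 or lower, which the row equates with ANC above 1.0. For low platelets it is to withhold until the count is at least 25 Gi/L and any bleeding has resolved. Each of the three hold rows resumes at the same dose on first occurrence.

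**The concern.** A site managing a Cycle 1 DLT can find two instructions for one event. Under 6.7.2 both drugs normally stop. Under the tables, duvelisib is held and restarted with no benefit or agreement condition, and in some rows at a blood count that 6.7.2 would not accept.

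This is the first clinical study of duvelisib with a PD-1 inhibitor, and Section 2.4.1 lists neutropenia among the important identified risks of duvelisib. What is at stake is whether a subject with a serious early toxicity is re-exposed safely, and in the same way at every site.

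**Working it through.** No sample size, power or alpha figure is involved. The check matches each DLT type in 6.7.1 to its row in Tables 10, 12 and 13 and compares action and restart level with 6.7.2, using the grade labels printed in the protocol.

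**Rows where the recovery level differs from baseline or Grade 1** (all in Table 12)

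| Event | Restart level | Grade at restart | Gap to Grade 1 |
|---|---|---|---|
| ANC below 0.5 | ANC above 0.5 | Can still be Grade 3, since Grade 2 or lower is given as ANC above 1.0 | up to 3 − 1 = 2 |
| Febrile neutropenia, Grade 3-4 | Afebrile and ANC above 1.0 | 2 or lower | up to 2 − 1 = 1 |
| Platelets below 25, or 25 to below 50 with Grade 2 bleeding | Platelets at least 25, and bleeding resolved if applicable | Can be Grade 3 (25 to below 50 is labelled Grade 3) | up to 3 − 1 = 2 |

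The baseline alternative in 6.7.2 does not close these gaps. Section 5.1 requires ANC of at least 1.5 and platelets of at least 100 at entry. In the bleeding part of the platelet row, 25 is already met at onset, so the row asks for resolution of bleeding but no rise in platelets.

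**Rows where only stop versus hold differs**

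- Grade 3 diarrhea or colitis, Grade 3 cutaneous reactions (Table 10, and Table 12 for the lead-in) and Grade 3 or higher infection (Table 12): the tables require resolution, which is at least as strict as Grade 1.
- Grade 3 ALT/AST elevation in the lead-in: resume below 3 × ULN. Table 12 labels 3 to 5 × ULN as Grade 2, so this is Grade 1 or lower.

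**Rows that agree with the 6.7.2 default**

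Grade 3 or higher pneumonitis, life-threatening diarrhea or cutaneous reactions, SJS/TEN/DRESS, confirmed PJP and, on combination therapy without liver metastases, AST or ALT above 5 × ULN: the relevant row discontinues treatment.

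**A DLT with no hold**

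Grade 3 or higher neutropenia with infection is a DLT whatever the grade of infection. With ANC 0.5 to 1.0, Table 12 keeps the dose, and its general infection row starts at Grade 3. An infection below Grade 3 that is not covered by the CMV, PJP or febrile neutropenia rows therefore triggers no interruption in the table.

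**Table 13**

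For some Grade 3 or 4 endocrine events (hypophysitis, thyroid disorders, hyperglycemia), pembrolizumab may be withheld until the subject is clinically stable. This is an ungraded standard. It matters here only if the event is judged at least possibly related to duvelisib and so can be a DLT.

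**Precedence**

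No sentence in 6.6, 6.7 or 7.1 ranks the texts. Section 7.1 lists unacceptable toxicity as the Investigator defines it, but not a DLT.

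**Why the choice matters in practice**

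A DLT by day 28 followed by the maximum 42-day hold runs to 28 + 42 = day 70. The first scheduled Stage 1 scan is at 10 weeks, 10 × 7 = day 70. Scheduled imaging will rarely supply evidence of benefit before a restart decision, so 6.7.2 would usually stop a subject whom the tables would usually restart.

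**The case against.** The strongest reply is that 6.7.2 is addressed specifically to subjects with a DLT, while the tables are recommendations for all subjects and cycles and are needed for non-DLT events. A specific rule normally overrides a general one. That is the likely intent, and it removes most of the conflict for a careful reader. But 6.7.2 is itself hedged, and the override has to be inferred.

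Other text also helps:
- Section 8 asks that urgent safety concerns be discussed with the Sponsor immediately.
- Section 7.1 lets the Investigator stop for unacceptable toxicity whatever a table recommends.
- Section 6.7.1 lets the Investigator and Sponsor document that an event within the definition is not a DLT, which could cover low-grade infection with ANC 0.5 to 1.0.
- The platelet row requires bleeding to resolve.

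These points lower the risk, but none sets the restart level. The sentence in 6.6.2 that lets pembrolizumab continue during a duvelisib hold adds no separate conflict. If duvelisib is discontinued, 6.6.2 also stops pembrolizumab, in line with 6.7.2.

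Three stronger readings are not supported. A reader might infer that recovery levels clash across all toxicities; the row check shows otherwise. A reader might infer that a thrombocytopenia DLT needs no platelet recovery; the general recovery sentence in 6.7.2 still implies it. A reader might also want a probability that a subject is affected; the documents give neither a DLT rate nor a split by type, so any figure would be assumed.

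**Conclusion.** The protocol is wrong as written on this point, at a minor level and for patient safety only. Some events that qualify as DLTs have two operative rules with no stated precedence. Within Tables 10 and 12 the restart levels differ in three hematologic rows, by up to one or two grades. One neutropenia DLT can continue without a hold unless it is documented as not a DLT. Table 13 adds an ungraded standard for a duvelisib-related DLT of the kinds it covers. The hemoglobin wording for thrombocytopenia is an error whichever text governs.

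A reader might infer that the 6-subject decision or the efficacy test is compromised. It is not: an event counts as a DLT however the subject is later managed, and the Simon stage sizes and cut-offs do not depend on restart rules. The mismatch by which Section 4.1 sends unacceptable toxicity to 6.6 and the Table 7 footnote sends it to 6.7 is clerical.

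The conclusion rests on the protocol's printed grade labels and entry criteria, not on any assumed event rate.

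**What to change.** 1. State in 6.7.2, with a note to Tables 10, 12 and 13, that 6.7.2 governs any event judged a DLT. Any restart must meet the stricter of the 6.7.2 and table recovery levels, so that resolution still applies to infection, cutaneous reactions and diarrhea, and baseline or Grade 1 applies to ANC and platelets. Dose reductions and discontinuations in the tables still apply.
2. Rewrite the last sentence of 6.7.2 so that a thrombocytopenia DLT requires platelet recovery and a low-hemoglobin DLT requires hemoglobin recovery.

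The two cross-references for unacceptable toxicity can be aligned in the same edit. The cost is one short paragraph, three table notes and one corrected sentence, with no added procedures or subjects.

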6.8. Intervention after the End of the Study

Subjects receiving clinical benefit from duvelisib in combination with pembrolizumab therapy may continue receiving treatment until either the final analysis of the ORR endpoint has been completed or all active subjects have been followed for 1 year after entry of the last subject, whichever is later. If the study is ended before all subjects discontinue treatment, any subject continuing to receive benefit will be provided the opportunity to continue to receive study intervention. However, in any case, the total duration of therapy will not exceed 24 months.

7. DISCONTINUATION OF STUDY INTERVENTION(S) AND SUBJECT DISCONTINUATION/WITHDRAWAL

7.1. Discontinuation of Study Interventions

Study interventions will be discontinued for any of the following reasons:

- Subject withdrawal of informed consent
- Protocol-specified disease progression
- Clinical deterioration (at the discretion of the Investigator)
- Duvelisib interruption for > 42 days due to duvelisib-related toxicity, unless approved by study Medical Monitor
- Unacceptable toxicity (as defined by the Investigator)
- Pregnancy
- Termination of the study by the Sponsor
- Death
- Maximum treatment duration of 24 months is reached
- Other reasons, including major protocol violation or noncompliance

The Investigator must determine the primary reason for discontinuation of study intervention(s) and record this information in the CRF.

Subjects who discontinue the study interventions (i.e., duvelisib and pembrolizumab) will complete an EoT Visit and should continue in the study so that follow-up information on survival status may be obtained (See Section 8.1.3). See the SoA ([Table 1](#) and [Table 3](#)) for data to be collected at the time of discontinuation of study interventions and during follow-up and for any further evaluations that need to be completed.

Discontinuation of specific sites or of the study as a whole are described in Section [10.6.8](#).

7.2. Subject Withdrawal from the Study

- A subject may withdraw from the study at any time at his/her own request or may be withdrawn at any time at the discretion of the Investigator for safety, behavioral, compliance, or administrative reasons.
- If a subject withdraws during the treatment phase, an EoT Visit should be conducted, if possible, as described in the SoA ([Table 1](#) and [Table 3](#)).
- Additional visits may be conducted as necessary for any abnormal findings that require medical follow-up.
- The subject will be permanently discontinued from the study interventions and withdrawn from the study at that time.
- If the subject withdraws consent for disclosure of future information, the Sponsor may retain and continue to use any data collected before such a withdrawal of consent.

- If a subject withdraws from the study, he/she may request destruction of any samples taken and not tested, and the Investigator must document this in the site study records.

7.3. Lost to Follow-up

A subject will be considered lost to follow-up if he or she repeatedly fails to return for scheduled visits and is unable to be contacted by the study site.

The following actions must be taken if a subject fails to return to the clinic for a required study visit:

- The site must attempt to contact the subject and reschedule the missed visit as soon as possible. If contact with the subject is made, the site should counsel the subject on the importance of maintaining the assigned visit schedule and ascertain whether or not the subject wishes to and/or should continue in the study.
- Before a subject is deemed lost to follow-up, the Investigator or designee must make every effort to regain contact with the subject. These contact attempts (e.g., 3 phone calls followed by a certified letter) should be documented in the subject's medical record.
- Should the subject continue to be unreachable, he/she will be considered to have withdrawn from the study.

8. STUDY ASSESSMENTS AND PROCEDURES

- Study procedures and their timing are summarized in the SoA ([Table 1](#), [Table 2](#), [Table 3](#), and [Table 4](#)). Protocol waivers or exemptions are not allowed.
- Urgent safety concerns should be discussed with the Sponsor immediately upon occurrence or awareness to determine if the subject should continue or discontinue study intervention(s).
- Adherence to the study design requirements, including those specified in the SoA, is essential and required for study conduct.
- All screening evaluations must be completed and reviewed to confirm that potential subjects meet all eligibility criteria. Screening activities will be performed within 30 days before the first dose (C1D1). Repeat laboratory assessments during the Screening Period do not constitute rescreening. The Investigator will maintain a screening log to record details of all subjects screened and to confirm eligibility or record reasons for screen failure, as applicable.
- Procedures conducted as part of the subject's routine clinical management (e.g., blood count) and obtained before signing of the ICF may be used for screening or baseline purposes provided the procedures met the protocol-specified criteria and were performed within the time frame defined in the SoA.
- The maximum amount of blood collected from each subject over the duration of the study, including any extra assessments that may be required, will be described in the ICF. Repeat or unscheduled samples may be taken for safety reasons or for technical issues with the samples.

